### **9.3. Time Period and Frequency for Event Assessment and Follow-up**

The investigator, or designated individual, will record all reportable events with start dates occurring any time after informed consent is obtained. At each study visit, the investigator will inquire about the occurrence of AE/SAEs since the last visit.

All AE/SAEs need to be followed until the event is resolved (with or without sequelae). The medical monitor or designee of this clinical investigation will decide if more follow up information is needed in case the event is not resolved at study completion. All required treatments and outcomes of the SAE must be recorded in the eCRF.

### **9.4. Reporting Procedures**

#### **9.4.1. *Adverse Event Documentation and Reporting Requirements***

Subjects should be encouraged to report AEs spontaneously or in response to general, non-directed questioning (e.g. "How was your health been since last visit?"). Anytime during the study, the subject may volunteer information that resembles an AE.

Each AE must be reported to the sponsor regardless of classification, seriousness, intensity, outcome or causality. The investigator is responsible for ensuring that all AEs observed by the investigator, or reported by the subject, that occur from the time that the subject has signed the informed consent through the end of the study are properly assessed, recorded, and reported as defined and described in the AEs, Adverse Device Effects and Device Deficiencies section of this protocol. All adverse events must be documented by completing subject's medical records (source documents) and appropriate eCRF by the investigator or study coordinator throughout the study and provided to the Sponsor. All AEs will be monitored until they are adequately resolved or explained.

Anonymized documentation pertaining to the AE (e.g. laboratory tests, consultation reports, post-mortem reports, new information relating to a previously reported AE, correspondence with the local EC, etc.) will be provided by the investigator to the sponsor or designee in a timely manner, when requested. Follow-up reports relative to the subject's subsequent course must be submitted to the sponsor or designee until the event has resolved or, in case of permanent impairment, until the condition stabilizes. If the subject is withdrawn from the study because of the AE, the information must be included on the appropriate eCRFs.

The sponsor is responsible for the classification of AEs and ongoing safety evaluation of the study and shall review the investigator's assessment of all AEs. The sponsor will determine and document in writing their seriousness and relationship to the investigational device. In case of disagreement between the sponsor and the principal investigator(s), the sponsor shall communicate both opinions to the concerned parties.

Biosense Webster will ensure that investigators are instructed to return devices suspected of causing an AE or SAE (i.e., definitely device-related or possibly device-related) in accordance with relevant regulations and current company procedures.

In the case of serious device effects and device deficiencies that could have led to serious adverse device effects, the Sponsor will determine whether the risk analysis needs to be updated and whether corrective or preventative action is required.

Timing for reporting the different types of AEs is described in Table 9.

**Table 9 AE Reporting Requirements**

Type of Adverse Event	Reporting Requirements
Serious Adverse Events	Report to Sponsor immediately upon awareness of event but no later than 72 hours
USADE & SADE	Report to Sponsor immediately upon awareness of event but no later than 72 hours
Primary AEs	Report to Sponsor immediately upon awareness of event but no later than 72 hours
Study device failure/malfunction associated with an AE	Report both study device failure and AE to Sponsor immediately upon awareness of event but no later than 72 hours
All other Adverse Events	Report to Sponsor within 2 weeks upon awareness of the event

#### **9.4.2. *Serious Adverse Events Reporting***

All SAEs, whether or not they are related to the device or procedure, must be reported to the Sponsor, via eCRF, immediately upon awareness of event but no later than 72 hours by the study site personnel.

The study investigator shall report the SAE and device deficiencies that could have led to SAE to the reviewing EC in accordance with the local EC requirements. The Sponsor will ensure that investigators are instructed to return devices suspected of causing an AE or SAE (i.e., definitely device-related or possibly device-related) in accordance with relevant regulations and current company procedures.

In the case of serious device effects and device deficiencies that could have led to serious adverse device effects, the Sponsor will determine whether the risk analysis needs to be updated and whether corrective or preventative action is required.

The sponsor will submit as per site specific requirements to all participating clinical investigators, an update of all SAEs and all device deficiencies that could have led to a SAE occurring to all participating sites. Event reporting to relevant regulatory authorities for non- CE marked devices per MEDDEV 2.7/3 Rev3 guidelines will occur by the sponsor and if indicated per local country requirements by the investigator. Pursuant to EN ISO 14155: 2011 all SAEs will be fully recorded and reported by the sponsor to the regulating Ministry of Health (MOH) as well as the EC according to the deadlines in force.

#### **9.4.3. *Unanticipated Device Effect Reporting***

All UADE/SADE/USADE must be reported to the Sponsor, via eCRF, immediately upon awareness of event but no later than 72 hours by the study site personnel. An investigator shall submit to the reviewing EC a report of any unanticipated adverse device effect occurring during an investigation according to EC requirements.

#### **9.4.4. *Events of Special Interest***

All study device failure/malfunction must be reported to the Sponsor, via eCRF, as soon as possible within 72 hours by the study site personnel. If a device failure is detected or suspected, it should be documented on the eCRF and the device returned according to the Sponsor's instructions.

The investigational device should be sent to appropriate R&D team or designated Quality engineer and should be reported to the medical safety lead. Complaints related to non-investigational products manufactured and/or distributed by Biosense Webster, used during the procedure related to other devices (other than the study device under investigation), are to be reported according to current Biosense Webster procedures and other policies as necessary (i.e., institutional policies, EC policies, and local regulations), investigators are instructed to return devices in accordance with current company procedures and other relevant regulations.

Event reporting to relevant competent authorities in accordance with the jurisdictional regulations will occur by the sponsor and/or by the investigator, depending upon the local requirements and will be done in EU per MEDDEV 2.12/1 guidelines for CE-marked devices manufactured by Biosense Webster and per MEDDEV 2.7/3 guidelines for non-CE-marked devices manufactured by Biosense Webster.

A device deficiency related to a medical device not manufactured by Biosense Webster should be reported by the investigator to their respective manufacturer as per relevant regulation. Complaints related to non-Biosense Webster, Inc. products must be handled according to institutional policies, EC policies, and local regulations.

#### **9.5. Safety Oversight**

Safety oversight will be conducted as described in the safety management plan. Aggregate safety data will be reviewed during enrollment by the study safety lead in order to promptly identify new issues or trends which may have an impact on the conduct of the study and/or subject safety. Under the rules of an approved study-specific charter, safety events will be reviewed by an established committee which may recommend appropriate action(s) to ensure subject safety.

### **10. Administrative Responsibilities**

#### **10.1. Ethics Committee and Competent Authority Application**

The study protocol (or amendment[s]), ICF, and other applicable study related documents must be approved by the Ethical Committee (EC) and Competent Authorities (CA) before enrollment of subjects. Any additional requirement imposed by the EC or regulatory authority shall be discussed, agreed upon, and followed. A signed copy of the EC and CA approval letters addressed to the investigator must be submitted to Biosense Webster certifying study approval prior to subject enrollment. Biosense Webster and the EC must approve, in writing, any changes to the protocol that affect the rights safety and/or welfare of the subjects, or may adversely affect the validity of the study.

In addition, Biosense Webster, Inc. is responsible for notifying the relevant CA of the intention to perform a clinical investigation under this protocol and ensure to get the official response/ approval before starting the clinical investigation.

## 10.2. Audits and Inspections

The sponsor and/or designee and/or Regulatory Authorities may contact the participating institution to inform the investigator of an upcoming audit/inspection. The investigator should immediately notify the sponsor of any Regulatory Authority audits/inspection at the study site. The audit/inspection can include the review of documents, facilities, records and any other resources deemed by the authorities to be related to study.

## 11. Deviations from the Clinical Study Plan

The investigator is responsible for ensuring that the clinical investigation is conducted in accordance with the procedures and evaluations described in this protocol. The study monitors shall verify that the conduct of the study is in compliance with the currently approved protocol and applicable regulations, and shall identify any issues of non-compliance with regulations or guidelines.

Issues of non-compliance include but are not limited to repeated protocol deviations; failure to obtain proper informed consent; non-conformance to EC requirements; failure to report Adverse Events, product malfunctions and other product issues; and other non-conformance to GCP.

A protocol deviation is defined as an instance of failure to follow, intentionally or unintentionally, the requirements of the protocol (e.g. missed test or procedure, visit out of window, non-adherence to inclusion/exclusion criteria). Investigators are not allowed to deviate from the protocol. Protocol deviations will be monitored closely and will be reported per EC/CA requirement.

Under emergency circumstances, deviations from the protocol to protect the rights, safety and well-being of a subject may proceed without prior approval of the sponsor and EC. Such deviations shall be documented and reported to the sponsor and the EC as required.

All instructions described in this study protocol are to be followed. If an amendment is required, it must be made in written form and receive approval from all persons and authorities who approved the original protocol. Administrative changes (do not affect subject's benefits/risks ratio) may be inserted with abbreviated approval. All amendments will be distributed to all original protocol recipients.

## 12. Investigational Product Accountability

### 12.1. Use of the Investigational Device and Investigator Experience

In addition to the clinical protocol training (i.e. during the site initiation visit), all investigators who will be performing the ablation procedures for this study will be required to attend both a didactic session, which includes detailed reviews of the study catheter (specifications, parameters, etc.) and the results of the preclinical studies completed. Ablating physicians with no prior in human experience with multi-ablation catheter will also receive hands-on training using the THERMOCOOL SMARTTOUCH® SF-5D catheter. The combination of the didactic and hands-on (in-vitro and/or in-vivo) portions of the documented device training will provide the investigator with the experience necessary to perform the protocol specified procedures for the study.

Investigators selected will be highly skilled in intracardiac mapping and AF ablation with RF ablation catheters.

## 12.2. Materials

Biosense Webster, Inc., Irwindale, CA USA, has manufactured the catheters to be used in this study. The investigational devices were built in a clean room environment, and sterilized using EtO gas, in a manner similar to standard, commercially approved Biosense Webster products.

Complete manufacturing records of every lot of catheter manufactured for human use during this study are maintained at Biosense Webster, Inc. Each lot of catheters is released for human use under a Confirmation of Conformity from Regulatory Affairs that will certify that the investigational catheters conforms to the Essential Requirements for product release apart from those features that are being investigated in this clinical investigation. And that, with regard to these aspects, every precaution has been taken to protect the health and safety of the patient.

## 12.3. Device Acquisition and Accountability

After obtaining a fully executed clinical trial agreement and appropriate competent authority (CA)/ethical committee (EC) approvals, the study site will receive the necessary amount of study-related materials prior to commencement. Study-related devices (investigational 'THERMOCOOL SMARTTOUCH® SF-5D catheters' and non-investigational devices) will be shipped to the site upon completion of required documentation.

Investigational Study Devices will be labeled as "Investigational Device" and are only to be used for subjects enrolled in this clinical study.

The Sponsor will keep records of all investigational devices shipped to the site.

Investigational site personnel is responsible for appropriate logging of devices received, verification of packing slip information (i.e. lot numbers and quantity shipped) and date, and identifying that each device was used in the study and disposition information completed when returned to the Sponsor. The Sponsor will label all investigational devices as "Investigational device" in a prominent location.

The Investigational Device Accountability Log shall record the following information:

- Date of receipt
- Person in receipt of the devices
- Quantity received
- Catalog number for catheters
- Serial/lot numbers
- Expiry Date
- Date devices was used
- Subject ID on whom device was used
- Date of return

## 12.4. Device Returns

All investigational devices 'THERMOCOOL SMARTTOUCH® SF-5D catheters' (used and unused) will be returned to the Sponsor's attention at the below address. Any suspected malfunctioning device or device associated with an adverse event (device related or possibly device related) will undergo a thorough complaint analysis and must be properly documented on the electronic case report form (eCRF).

All returned devices must be properly labeled with the subject identification number, date of issue, identified as a defective return, non-defective return, or adverse event (as applicable).

All tracking information must be retained in the event the package has been lost and requires tracking.  
All investigational devices should be returned to:

ATTN: Complaints Lab  
Biosense Webster, Inc.  
[name]  
[name]

## 12.5. Device Labeling

Sample labels are included in the package approved by the Regulatory/Competent Authorities. All labeling clearly identifies the product as investigational.

## 13. Clinical Monitoring

Clinical site monitoring is conducted to ensure that the rights and well-being of human subjects are protected, that the reported trial data are accurate, complete, and verifiable, and that the conduct of the trial is in compliance with the currently approved protocol/amendment(s), with GCP, and with applicable regulatory requirement(s). Each site will undergo periodic monitoring of the study, which involves a visit from a Sponsor representative, qualified to perform such visit.

Monitoring visits may include, but are not limited to, the following:

- Protocol adherence
- Source documentation verification and accuracy of the eCRFs
- Verification that informed consent is being obtained for all subjects participating in the study in accordance with requirements described in the study protocol
- Verification of completeness of the Site File
- Verification of accuracy of all study logs such as the Delegation of Responsibility Log, etc.
- Compliance with applicable regulations
- Identification and action to resolve any issues or problems with the study.

Data are to be submitted promptly via e-CRF after collection. Missing or unclear data will be corrected as necessary throughout the trial. Biosense Webster will request further documentation such as physician and/or cardiac EP lab procedure notes when complications or malfunctions are observed and reported.

Further details on clinical monitoring are provided in the study specific monitoring plan.

## 14. Statistical Methodology

### 14.1. Study Design

The QDOT-FAST study is a prospective, multi-center, non-randomized, interventional clinical study.

### 14.2. Treatment Assignment

All subjects in the study will be treated with the THERMOCOOL SMARTTOUCH® SF-5D Catheter (D-1395-05-SI).

### 14.3. Interval Windows

See Section 8.8.

### 14.4. Primary and Secondary Endpoints, and Associated Hypotheses

#### 14.4.1. Primary Endpoints and Associated Hypotheses

The primary safety endpoint is acute safety defined as the Primary Adverse Events (PAEs) within the first 7 days. PAEs include the following AEs:

Atrio-Esophageal Fistula*	Phrenic Nerve Paralysis
Cardiac Tamponade/perforation	Pulmonary Vein Stenosis*
Death*	Stroke/CVA
Major Vascular Access Complication/Bleeding	Thromboembolism
Myocardial Infarction	TIA

\*Device or procedure related death, pulmonary vein stenosis and atrio-esophageal fistula that occur greater than one week (7 days) post-procedure are considered and analyzed as primary AEs.

The primary effectiveness endpoint is acute procedural success defined as achieving confirmation of entrance block in all targeted PVs after adenosine and/ or isoproterenol challenge. The use of non-study catheter for PVI will be considered as an effectiveness failure.

No formal statistical hypotheses will be formulated and performed for the primary endpoints.

#### 14.4.2. Secondary Endpoints and Associated Hypotheses

No formal statistical hypotheses will be formulated and performed for the secondary endpoints. The secondary safety and procedural endpoints are listed below.

##### Safety

- Incidence of Serious Adverse Device Effects (SADEs)
- Incidence of Serious Adverse Events (SAEs) within 7 days (early-onset), >7-30 days (peri-procedural) and >30 days (late onset) of initial ablation procedure
- Incidence of non-serious adverse events
- Incidence of pre-and post-ablation asymptomatic and symptomatic cerebral emboli as determined by MRI evaluations
- Incidence of new or worsening neurological deficits compared to baseline
- Summary of NIHSS, mRS and MoCA scores at baseline and follow-up timepoints

#### **Effectiveness**

- PVI achieved with TGA mode only among all targeted veins and by subject
- PVI achieved with combined use of TGA and Q-mode among all targeted veins and by subject
- Ablation of acute reconnection (touch-up) among all targeted veins and by subject
- Touch-up applications with TGA, Q-mode and non-study catheter applications
- PV ablation by a non-study catheter among all targeted veins and by subject

#### **Additional analyses on procedural data, including but not limited to:**

- Use of QDOT Micro™ catheter ablation outside the PV area
- Use of a non-study catheter for ablation outside the PV area
- Total procedure time, mapping time, PV ablation time, total ablation time, RF application time, LA dwell time
- Total number of RF applications, % TGA applications and % Q-mode applications
- Anatomical location of touch-up applications
- Temperature, power, contact force, impedance
- Total Fluoroscopy time/dose

### **14.5. Levels of Significance**

There are no formal hypothesis tests for this study. All confidence intervals will use two-sided 95% confidence unless otherwise stated.

### **14.6. Analysis Sets**

The following analysis populations will be used to complete the analyses of data:

- **Safety Population:** The safety population will include all enrolled subjects who have the investigational device inserted, regardless if RF energy is delivered.
- **Effectiveness Population:** The effectiveness population will include all enrolled subjects who have had the investigational device inserted and underwent ablation with the study catheter used in conjunction with TGA mode for PVI. The subjects without any TGA mode application for PVI will be excluded from the effectiveness population.
- **Neurological Assessment Evaluable (NAE) Population:** The NAE Population will include all enrolled subjects who meet the eligibility criteria, have been treated with the study catheter and had any post-ablation neurological assessment. Assessment of incidence of new lesions or deficits requires availability of the associated pre-procedural assessment.

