#### 1.4.1. *Known Potential Risks*

## Known Potential Risks associated with catheter RF ablation procedure

The risk of pulmonary adverse events (e.g., PV stenosis, thrombus and cardiac perforation) associated with an AF ablation procedure targeting the pulmonary veins is considered small (<4%).

Arterial or venous injury, including arterial dissection, thrombosis, occlusion or hemorrhage at the catheter insertion sites or at other sites along the vessels can occur (risk <1%). These types of injuries may cause hemorrhage, hematoma or ischemic injury to an extremity or major organ.

RF current may cause **occlusion of a coronary artery**, either by direct thermal damage, spasm, or thrombosis. Experience at numerous clinical sites/centers suggests that the risk of coronary occlusion is less than 0.5%. Coronary arterial occlusion could produce myocardial infarction (MI), angina or death.

The application of RF current close to the AV node or HIS bundle could **damage or destroy the normal AV conduction system**, producing complete heart block and requiring implantation of a permanent pacemaker.

A thrombus may form on the ablation electrode during the application of RF current, usually indicated by an impedance rise; however, this can also occur in the absence of an impedance rise. The thrombus could become dislodged and embolize to produce a stroke, myocardial infarction (MI), or other ischemic injury. The possible embolic sources include thrombus formation on the ablation catheter tip and sheath, debris from steam pop and charring, preexisting thrombus in the heart and air embolus. The risk of an embolus is reduced by quickly terminating the application of

current after an impedance rise, which limits the size of the coagulum on the electrode. Probably the most important aspect of the THERMOCOOL® family of catheters is the absence or very low likelihood of thrombus formation during RF.

**Thrombus formation on the endocardium** following ablation may produce an arterial or pulmonary embolus. This risk may be reduced using aspirin or other anticoagulant therapy, at the discretion of the investigator.

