## 4.4. Subject Enrollment Disposition

The following subject groups are defined:

- **Enrolled Subjects:** Patients who sign the informed consent form.
- **Excluded Subjects:** Subjects who are enrolled but never undergo insertion of the study catheter. Excluded subjects will only be followed between ICF signature and exclusion for event reporting.

- **Evaluable Subjects:** All enrolled subjects who have the study catheter inserted.
- **Discontinued Subjects:** Enrolled subjects who have the study catheter inserted but do not undergo ablation (i.e., no RF energy is delivered with the study catheter). Discontinued subjects will remain in follow-up for 30 days.
- **Lost to Follow-up Subjects:** Evaluable subjects of which contact is lost after most recent visit (despite 3 documented attempts to contact the subject).
- **Withdrawn / Early Termination Subjects:** Subjects who withdraw consent for study participation or are withdrawn by the investigator, are terminated from the study prior to completion of all follow-up visits.
- **Completed Subjects:** Enrolled subjects who have not been excluded, discontinued, expired, withdrawn, terminated early, or lost-to-follow-up from the study prior to the final study visit.

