#### **14.8.4.3. Analyses of Secondary and Additional Endpoints**

No formal statistical hypotheses and inferential statistics will be formulated and performed for the secondary and additional endpoints. Details of analyses methods for secondary and additional endpoints will be provided in SAP.

Secondary Safety analysis for SADEs and AEs will be performed on the Safety Population. The neurological assessment related endpoints will be analyzed in the NAE population. Secondary Effectiveness (including Procedural Data) will be performed on the Effectiveness Population.

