5.2 Secondary Endpoints

- **Safety**
 - Incidence of Serious Adverse Device Effects (SADEs)
 - Incidence of Serious Adverse Events (SAEs) within 7 days (early-onset), >7-30 days (peri-procedural) and >30 days (late onset) of initial ablation procedure
 - Incidence of non-serious adverse events
 - Incidence of pre-and post-ablation asymptomatic and symptomatic cerebral emboli as determined by MRI evaluations
 - Incidence of new or worsening neurological deficits compared to baseline
 - Summary of NIHSS, mRS and MoCA scores at baseline and follow-up timepoints
- **Effectiveness**
 - PVI achieved with TGA mode only among all targeted veins and by subject
 - PVI achieved with combined use of TGA and Q-mode among all targeted veins and by subject
 - Ablation of acute reconnection (touch-up) among all targeted veins and by subject
 - Ablation by a non-study catheter among all targeted veins and by subject
 - Touch-up applications with TGA, Q-mode and non-study catheter applications
- **Additional analyses on procedural data, including but not limited to:**
 - Use of QDOT Micro™ catheter ablation outside the PV area
 - Use of a non-study catheter for ablation outside the PV area

- Total procedure time, mapping time, PV ablation time, total ablation time, RF application time, LA dwell time
- Total number of RF applications, % TGA applications and % Q-mode applications
- Anatomical location of touch-up applications
- Temperature, power, contact force, impedance
- Total Fluoroscopy time/dose

6 Levels of Significance

All data will be summarized by descriptive analyses. No formal statistical inference will be made. Sub-analyses will be done for subjects where TGA was the only application mode used and for subjects where applications were done through a combination of TGA and Q-mode. Where confidence intervals are used they will be two-sided 95% confidence intervals, unless stated otherwise.

7 Analysis Sets

The following analysis populations will be used to complete the analyses of data:

- **Safety Population (SP):** The safety population will include all enrolled subjects who have the investigational device inserted, regardless if RF energy is delivered. All safety analyses will be performed on the Safety Population.

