- **Effectiveness Population (EP):** The effectiveness population will include all enrolled subjects, have had the investigational device inserted and underwent ablation with the study catheter used in conjunction with TGA mode for PVI. The subjects without any TGA mode application for PVI will be excluded from the effectiveness population. All effectiveness analysis will be performed on the Effectiveness Population.
- **Neurological Assessment Evaluable (NAE) Population:** The NAE Population will include all enrolled subjects have been treated with the study catheter and have any post-ablation neurological assessment. Assessment of incidence of new lesions requires availability of pre-and post MRI. The subjects without pre-MRI but no lesion on post-MRI will be included in the NAE population. Assessment of incidence of new deficits requires availability of pre-and post-neurological evaluation. Analysis of neurological data will be performed on the NAE Population.

8 Sample Size Justification

This is a clinical feasibility study for evaluation of safety and acute performance of THERMOCOOL SMARTTOUCH® SF-5D system with TGA mode application for PVI. This clinical investigation is intended to provide preliminary estimates of safety and acute performance. Enrollment in the clinical investigation will be approximate 50 subjects,

distributed over up to 10 centers in Europe. Minimum attrition is expected for safety assessment. No more than 10% attrition is expected to assess effectiveness outcomes.

Because this study is a feasibility study, there is no statistical power calculation and no hypothesis to be tested. 50 subjects are deemed sufficient to clinically characterize safety and acute outcomes.

9 Data Monitoring Committee (DMC)

Safety review will be performed by the medical safety officer as described by Safety Management Plan.

10 Analyses to be Conducted

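### As most naturally read, the neurological (NAE) set leaves out subjects who had the catheter inserted but received no study-catheter RF, so their scheduled MRI and neurological findings drop out of the secondary neurological tables

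*Protocol*

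**What the plan says.** Protocol 14.6 and SAP section 7 each list three analysis sets. In both, the Safety Population takes in enrolled subjects "who have the investigational device inserted, regardless if RF energy is delivered". The entry condition for the NAE population is different. The protocol admits eligible enrolled subjects who "have been treated with the study catheter and had any post-ablation neurological assessment". The SAP drops the eligibility condition but still requires that subjects "have been treated with the study catheter and have any post-ablation neurological assessment".

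Protocol 4.4 names the group that meets the first condition but, on the natural reading, not the second. These are the Discontinued Subjects: "Enrolled subjects who have the study catheter inserted but do not undergo ablation", which that section explains as no RF energy delivered with the study catheter. It adds that "Discontinued subjects will remain in follow-up for 30 days".

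On which set governs the results, Protocol 14.8.4.3 states: "The neurological assessment related endpoints will be analyzed in the NAE population". SAP sections 7 and 10.4 say the same. The endpoints concerned are MRI-detected cerebral emboli, new or worsening deficits, and the NIHSS, mRS and MoCA summaries. All are listed as secondary safety endpoints (Protocol 3.2.2 and 14.4.2, SAP 5.2). However, the Safety Population entry in SAP section 7 also assigns every safety analysis to the Safety Population, with no exception for neurological data.

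**The concern.** The trial counts safety from catheter insertion, but its neurological safety endpoints appear to be counted from RF delivery. That is a post-insertion exclusion. It conditions an embolic result on the procedure having gone far enough for study-catheter RF to be applied.

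Some embolic risk precedes RF. In its discussion of thrombus and embolism, Protocol 1.4.1 says "The possible embolic sources include thrombus formation on the ablation catheter tip and sheath", and the sentence goes on to include pre-existing cardiac thrombus and air. Those last two do not depend on RF. Protocol 8.2.2.4 also allows the study catheter to be used for mapping, so it may be in the left atrium for some time before any RF.

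What is at stake is mainly the silent lesion, which the mandated MRI before and after the procedure is there to detect. The adverse event definition in Protocol 9.1.1 does not mention asymptomatic imaging findings, so adverse event reporting cannot be relied on to pick them up. In a descriptive study of 50 subjects the counts are the result, and a change from one to none is visible.

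**Working it through.** The documents give no NAE size, expected emboli rate or discontinuation count, so there is no plan figure to reproduce. The check is a comparison of definitions, followed by an illustration of size.

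**Step 1. Where a Discontinued Subject falls**

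| Rule | Condition | Discontinued Subject |
|---|---|---|
| Safety Population (Protocol 14.6, SAP 7) | catheter inserted, RF not required | in |
| Post-procedure MRI, neurological exam, NIHSS (Protocol 8.2.4, Table 3) | within 72 hours after the procedure, no RF condition | scheduled |
| Stroke, TIA, thromboembolism as primary adverse events (Protocol 14.8.4.1, SAP 10.4) | Safety Population | counted |
| Other adverse events (Protocol 14.8.4.3, SAP 10.4) | Safety Population | counted |
| NAE population (Protocol 14.6, SAP 7) | treated with the study catheter, with a post-ablation assessment | out, if 'treated' means RF delivered |

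Nothing in either document adds these subjects back or provides a separate listing of their neurological findings.

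**Step 2. Does 'treated' mean RF delivered?** It is undefined, so this is an inference. Three points support it. The same list uses insertion wording where insertion is meant. Protocol 4.4 equates not undergoing ablation with no study-catheter RF. A subject who was never ablated cannot have a post-ablation assessment.

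**Step 3. Size**

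Inputs:
- N = 50 subjects with the catheter inserted (Protocol 4.3.2 and 14.7).
- Two-sided 95% intervals (Protocol 14.5).
- Discontinued Subjects: d = 1 or 2 (assumption).
- Event counts: assumption. All subjects are taken to have usable assessments.

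Rate as written = x/(50 − d), where x is the number of RF-treated subjects with a finding. Insertion-based rate = (x + y)/50, where y is the number of Discontinued Subjects with a finding. Exact (Clopper-Pearson) limits for k of n: lower = Beta(0.025; k, n − k + 1), upper = Beta(0.975; k + 1, n − k). For example:
- 0/49: upper = 1 − 0.025^(1/49) = 7.3%.
- 1/50: lower = 1 − 0.975^(1/50) = 0.05%; upper = Beta(0.975; 2, 49) = 10.6%.

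| d | x | y | As written | Insertion-based |
|---|---|---|---|---|
| 1 | 0 | 1 | 0/49 = 0% (0 to 7.3%) | 1/50 = 2.0% (0.05 to 10.6%) |
| 1 | 5 | 1 | 5/49 = 10.2% (3.4 to 22.2%) | 6/50 = 12.0% (4.5 to 24.3%) |
| 2 | 5 | 2 | 5/48 = 10.4% (3.5 to 22.7%) | 7/50 = 14.0% (5.8 to 26.7%) |
| 1 | 5 | 0 | 5/49 = 10.2% (3.4 to 22.2%) | 5/50 = 10.0% (3.3 to 21.8%) |

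One Discontinued Subject with a finding moves the rate by about 2 percentage points. One without a finding moves it by about 0.2 points the other way.

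**The case against.** The strongest reply is that 'treated' may simply mean 'had the study catheter used'. Protocol 14.2 says all subjects will be treated with it and adds no RF qualifier, and Protocol 4.4 defines Evaluable Subjects by insertion alone. That reading cannot be ruled out. It does not remove the problem, because the wording would then permit either set to be chosen after the data are seen.

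Second, the MRI endpoint is itself worded in terms of before and after ablation, so an ablated denominator is a coherent choice. This stands as a reason to keep showing the ablated subset, but not as a reason to report nothing on the others.

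Third, the study is descriptive, with no hypothesis or power calculation, and the intervals above overlap widely. That also stands: no error rate is affected.

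Three stronger readings are tempting and go beyond the documents:

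- *An embolic event that stopped the procedure would vanish from the safety results.* It would not. An event recognised during the procedure as stroke, TIA or thromboembolism is a primary adverse event in the Safety Population, and a new or worsened clinical finding is an adverse event under Protocol 9.1.1. A silent lesion is found only on the later MRI, so it cannot be the reason for stopping.
- *None of the listed embolic sources needs RF.* Protocol 1.4.1 introduces electrode thrombus as forming during RF application, and the same list includes debris from steam pops and charring. Pre-existing thrombus and air are the sources that clearly support the point.
- *Up to 5 of 50 subjects could be affected.* That would borrow the 10% attrition expected for effectiveness. The Effectiveness Population drops subjects with no TGA application for PVI, and a subject ablated only in Q-mode leaves that set but stays in the NAE set. For safety, Protocol 14.7 expects minimum attrition.

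**Conclusion.** The point holds within limits. On the most natural reading, both documents exclude Discontinued Subjects from the secondary neurological tables although their assessments are scheduled, and the SAP's general safety rule says otherwise. The loss is confined to those tables and is chiefly of silent MRI lesions; overt events remain in the primary and secondary adverse event results.

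The number affected is not given. Taking 0 to 2 of 50 as an assumption, the effect ranges from nothing to a few percentage points; the clearest case is 1/50 reported as 0/49. The direction is not fixed, since including a Discontinued Subject without a finding would slightly lower a non-zero rate. The conclusion rests on reading 'treated' as RF delivered. On the other reading, the defect is an undefined term plus two conflicting SAP rules, and the same edit settles both.

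**What to change.** In Protocol 14.6 and SAP section 7, define the NAE population as Safety Population subjects (study catheter inserted, whether or not RF was delivered) with any post-procedure neurological assessment. Keep the existing baseline requirement for new lesions and new deficits. Report the RF-treated subset as a supporting row in each neurological table. In SAP section 7, reconcile the sentence assigning all safety analyses to the Safety Population with the NAE rule there and in SAP 10.4, for example by naming the neurological endpoints as the exception. This definition would also remove the eligibility condition that now appears only in the protocol. That is a separate difference between the documents, and the sponsor should settle it explicitly.

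The cost is wording in two documents and one extra table row; no new tests are needed. The main denominator would include a few non-ablated subjects, which the supporting row makes visible. MoCA and mRS may be missing after baseline for these subjects. Neither is scheduled before discharge, the month 1 assessment is conditional on earlier neurological findings or symptoms, and 30-day follow-up ends inside the day 23 to 37 window. The score tables should state the number assessed at each time point.
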